## **E. Potential Scientific Problems**

Participant recruitment and retention may be a potential scientific concern; however, we have initial support from Naval command to recruit onboard an aircraft carrier (~5000 Sailors) and attached Striker units. The PI and [name] will continue to work with Naval command to ensure ongoing recruitment support and planning.

Technological issues with Android and/or iPhone platforms with the assigned study arms (Active or Control) may occur. The study team has pilot data that assists in problem-solving these concerns quickly. Cogito Corporation will have dedicated staff to assist with any Cogito Companion technological issues as they arise. The study team will monitor MyCAP issues and work closely with REDCap staff at the University in a timely manner. Issues will be documented and reviewed as part of Aim 2 and appropriate amendments may occur with consistently identified issues.

While 21% attrition is expected and the statistical methods proposed below are equipped to handle data that are missing at random, characteristics of participants who drop out of the study will be compared to those who do not and if there is differential dropout by group or it is plausible, based on characteristics of those who did drop out, that the missingness is related to the primary outcome of interest, additional methods aimed at accounting for nonignorable dropout will be employed where possible.

## F. Data Analysis Plan

**Power Analysis.** Power is calculated for the two primary hypotheses assessing episodes of distress and distress over the course of the study. We will recruit 1418 participants and expect approximately 33% to decline participation resulting in 950 participants randomized to either the Cogito Companion or Active Control groups, stratified by gender, force and phone type. Assuming 21% attrition, it is expected that 750 participants will complete the entire protocol. While the analysis will include all participants who are randomized, power is based on 750 completed (375 per group). Power to address episodes of distress was estimated using the Poisson regression procedure in Power and Sample Size (PASS) v13. An episode of distress is defined as an OQ-45 total score of  $\geq 64$  with each participant having a maximum of 6 possible episodes (every 2 weeks for weeks 2-12 of the study, inclusive). We wish to detect a 15% difference in the number of episodes of distress over the 3-month study period, and we assume a two-sided test and a significance level of 0.025 to control for the two primary tests (number of episodes and overall distress). If the Active Control mean response rate is 3.5 (i.e., number of episodes in the 3-month study period) we will have 97% power to detect a 15% difference. For Active Control response rates of 3, 2.5, 2 and 1.5, power is then 94%, 89%, 81% and 68%, respectively. For the second primary hypothesis, we will calculate the Area Under the Curve (AUC) using an estimate statement within a linear mixed model described below. We wish to demonstrate that the Cogito Companion is superior to Active Control by a margin of at least 14 points (minimally clinically significant difference, translates to an AUC difference of 84). Using the Superiority by a Margin procedure in PASS v13, 375 participants per group provides 90% power to demonstrate superiority, assuming a true difference of  $\geq 18.7$  points (AUC difference of 112.2) with a significance level of 0.025.

**Analysis Plan.** All analyses will assume a two-sided test of hypothesis, a significance level of 0.05 (unless otherwise indicated) and will be run in SAS v9.4 or higher, or R v3.3 or higher. To check randomization, demographic and clinical characteristics will be compared between groups using t-tests, chi-square tests or nonparametric tests, as appropriate. If any variable is found to be significantly different between the groups and is also plausibly associated with an outcome, it will be considered as potential confounders in the models described below.

**Aim 1.** To address the hypothesis regarding episodes of distress first using Poisson regression will be used to model the number (response rate) of episodes of distress as a function of group (0=Active Control, 1=Cogito), any potential confounders, and an offset of log (time) to account for varying lengths of follow-up. If the deviance is estimated to be  $> 1.5$ , Negative Binomial regression will be used instead, incorporating the same variables. The parameter estimate associated with the group variable will be exponentiated, providing an estimate of the ratio of response rates between the groups and will be reported with a 97.5% confidence interval (CI). To address the hypothesis regarding distress over the course of the study, a linear mixed-effects model will be employed with longitudinal OQ-45 scores as the dependent variable and group, potential confounders, and an interaction between group and time (using either natural cubic B-spline transformations on time or polynomial transformations on time) as independent variables. These transformations will also be applied to the random time effects so that individual trajectories can be calculated. Akaike's Information Criterion will be used to determine which model provides the best fit (both between the B-spline/polynomial models and within them). Once a final model is determined, the difference in AUC will be calculated and between groups and compared to the clinically meaningful AUC difference of 84 using a one-sided test. Here the null hypothesis is that  $AUC_{AC} - AUC_{Cogito} \geq 84$ , and the alternative hypothesis is that  $AUC_{AC} - AUC_{Cogito} < 84$ . The estimated difference will be reported with the one-sided 97.5% CI. For hypothesis 1.2, a Kaplan-Meier estimate will be used to compare the median time to treatment engagement

between the groups and each median will be reported with 95% CIs. Treatment engagement is operationalized as a visit with any medical or mental health provider in which a mental health related ICD code is identified. and will be determined by medical record review. Additionally, the total number of mental health visits calculated from the CSRI-EU-R will be modeled using a Poisson or Negative Binomial regression model to estimate the difference in number of visits between the groups over the course of the study. The model will be set up similarly to the OQ-45 model. Hypothesis 1.3 is similar to hypothesis 1.1 such that we wish to look at episodes of depressive symptoms (PHQ-9), post-traumatic symptoms (PCL-5) and suicide-related thoughts (BSS) as well as severity of each over the course of the study. We also wish to look at perceived physical and psychological health functioning (RAND SF-36) over the course of the study. The methods employed to address hypothesis 1.1 will be utilized to estimate the difference in number of episodes of each outcome (excluding the SF-36) as well as the difference in AUC for each outcome. Zero-inflated negative binomial regression will be considered for the BSS if a large proportion of the participants do not exhibit suicidal thoughts and transformations will be considered for the AUC BSS analysis, given that it is likely to be highly skewed. Cutoffs for episodes of depressive/post traumatic symptoms, and suicidal thoughts are  $\geq 10$  (PHQ-9),  $\geq 33$  (PCL-5), and  $\geq 2$  (BSS), respectively.

***Aim 2.*** We will assess the proportion of participants who find the Cogito Companion acceptable, defined as  $\geq 70\%$  of participants scoring  $\geq 24$  on the CSQ. The proportion of Cogito Companion participants with a CSQ score of  $\geq 24$  will be calculated with a 95% CI. Additionally, the proportion of participants engaging in activities will be reported with a 95% CI as well as the median (range) amount of time spent on the application. Feasibility will be measured by the proportion of Cogito Companion participants who complete treatment and reasons for termination will be examined.

***Exploratory Aim.*** To explore patterns of distress experienced by participants over the course of the study, individual OQ-45 curves modeled in Aim 1 will be qualitatively clustered into groups based on visual inspection of the trajectory patterns. Once distinct patterns are identified and labeled, baseline demographic and clinical characteristics of participants in each pattern will be summarized and reported. This will be performed for the entire sample, as well as within each group. This is considered a hypothesis generating aim. This analysis will be repeated for the PHQ-9, PCL-5, BSS and SF-36.

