## **I. Hypotheses and Specific Aims**

**Aim 1.** Evaluate the efficacy of the Cogito Companion as an upstream suicide prevention intervention.

**Hypothesis 1.1.** Participants allocated to the Cogito Companion will report significantly fewer episodes of distress and less distress over the course of the study (Outcome Questionnaire-45; OQ-45) compared to those allocated to the Active Control group.

**Hypothesis 1.2.** Among those with episodes of clinically meaningful distress, those allocated to the Cogito Companion will more rapidly engage in treatment (medical record review and Client Services Receipt Inventory-EU-Revised; CSRI-EU-R) to address such symptoms versus those allocated to the Active Control group.

**Hypothesis 1.3.** Participants allocated to the Cogito Companion will report significantly fewer episodes of and less severe depressive (Patient Health Questionnaire-9; PHQ-9) and post-traumatic symptoms (Post Traumatic Stress Disorder Checklist-5; PCL-5), and suicide-related thoughts (Beck Scale for Suicide Ideation; BSS, Columbia-Suicide Severity Rating Scale Screener; C-SSRS Screener), as well as overall increased perceived physical/psychological health functioning (Rand 36-Item Health Survey; SF-36) over the course of the study compared to those allocated to the Active Control condition.

**Aim 2.** Evaluate the acceptability and feasibility of the Cogito Companion among military personnel (Sailors).

**Aim 2.1.** Acceptability of Cogito Companion will evaluate based on participant satisfaction (CSQ), participant engagement in application-related activities (e.g., leaving voice recordings), and time spent on the application. Acceptability refers to the suitability of an intervention from the perspectives of the participants.

**Aim 2.2.** Feasibility of Cogito Companion will be evaluated based on participant retention and accrual, and number and type (minor, moderate, severe) of technical challenges noted during implementation. Feasibility refers to the ease of implementation.

**Exploratory Aim.** Identify patterns of distress, depressive symptoms, post-traumatic symptoms, suicide-related thoughts, and perceived physical and psychological health functioning over the course of the study among the entire sample, as well as within the Cogito Companion and Active Control groups.

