“Power Analysis. Power is calculated for the two primary hypotheses assessing episodes of distress and distress over the course of the study. We will recruit 1418 participants and expect approximately 33% to decline participation resulting in 950 participants randomized to either the Cogito Companion or Active Control groups, stratified by gender, force and phone type. Assuming 21% attrition, it is expected that 750 participants will complete the entire protocol. While the analysis will include all participants who are randomized, power is based on 750 completed (375 per group). Power to address episodes of distress was estimated using the Poisson regression procedure in Power and Sample Size (PASS) v13. An episode of distress is defined as an OQ-45 total score of ≥ 64 with each participant having a maximum of 6 possible episodes (every 2 weeks for weeks 2-12 of the study, inclusive). We wish to detect a 15% difference in the number of episodes of distress over the 3-month study period, and we assume a two-sided test and a significance level of 0.025 to control for the two primary tests (number of episodes and overall distress). If the Active Control mean response rate is 3.5 (i.e., number of episodes in the 3-month study period) we will have 97% power to detect a 15% difference. For Active Control response rates of 3, 2.5, 2 and 1.5, power is then 94%, 89%, 81% and 68%, respectively. For the second primary hypothesis, we will calculate the Area Under the Curve (AUC) using an estimate statement within a linear mixed model described below. We wish to demonstrate that the Cogito Companion is superior to Active Control by a margin of at least 14 points (minimally clinically significant difference, translates to an AUC difference of 84). Using the Superiority by a Margin procedure in PASS v13, 375 participants per group provides 90% power to demonstrate superiority, assuming a true difference of ≥ 18.7 points (AUC difference of 112.2) with a significance level of 0.025.

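### The two primary OQ-45 tests are powered for very different effects, and no planned AUC test can formally declare a benefit between 0 and 14 points

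*Protocol*

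**What the plan says.** Hypothesis 1.1 (Protocol, section I) expects the Cogito group to "report significantly fewer episodes of distress and less distress over the course of the study" than Active Control on the OQ-45. It names no margin.

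Protocol section F, Power Analysis, sets up two primary tests on that scale:

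- **Episodes.** "An episode of distress is defined as an OQ-45 total score of" 64 or more, with a "maximum of 6 possible episodes (every 2 weeks for weeks 2-12 of the study, inclusive"). The target is stated as "We wish to detect a 15% difference in the number of episodes of distress over the 3-month study period", two-sided at 0.025. Power is given as 97, 94, 89, 81 and 68% for control rates of 3.5, 3, 2.5, 2 and 1.5.
- **Overall distress (AUC).** "We wish to demonstrate that the Cogito Companion is superior to Active Control by a margin of at least 14 points", equated to an AUC difference of 84. Power is 90% at 0.025, "assuming a true difference of ≥ 18.7 points (AUC difference of 112.2") in the SAP's copy of the sentence.

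For both, "power is based on 750 completed (375 per group").

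Under Analysis Plan, Aim 1, the AUC difference is compared only with 84, one-sided, and reported with a one-sided 97.5% CI. The null there is AUC_AC − AUC_Cogito ≥ 84 and the alternative is < 84. Neither document gives an SD for the OQ-45 or the AUC, or relates the 15% to the 14 or 18.7 points.

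The SAP reproduces this text as the original plan. It says the team kept following it after the aims were revised.

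**The concern.** An episode is a dichotomy of the same score that the AUC averages, so an effect on one implies an effect on the other. A reader who sees 68–97% power beside 90% power may take both to describe one plausible effect of the app. If the effect is the one the episode test is sized for, the AUC test has almost no prospect of success while holding half of the 0.05.

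The margin also changes the question. Hypothesis 1.1 would be true if mean distress fell by 5 points, but the planned AUC test has no route to saying so. The trial could find fewer episodes and a clear mean reduction, and still have to report the second primary as not met.

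**Working it through.** **Inputs from Protocol section F (identical in the SAP).** N = 750, 375 per group (950 × 0.79 = 750.5). Control rates are 3.5 to 1.5 out of 6, with a rate ratio of 0.85 at two-sided 0.025. The margin is 14 points (14 × 6 = 84) and the assumed true difference is 18.7 points (18.7 × 6 = 112.2), with 90% power at 0.025.

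**Assumptions, not in the documents.** Scores are roughly normal, the treatment moves every score by the same amount, and the single-visit SD lies between about 20 and 30.

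**Step 1: reproduce the episode power.** For Poisson regression with a balanced binary covariate, power = Φ{[√(Nμ)·|ln 0.85| − z(0.9875)·√4] / √(2 + 2/0.85)}. At μ = 3.5 this is Φ{(51.23 × 0.1625 − 2.241 × 2)/2.086} = Φ(1.84) = 96.7%. The other rates give 93.9, 89.0, 80.7 and 67.9%. All match the plan.

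**Step 2: the SD implied by the 90%.** SD = (18.7 − 14)·√(375/2)/(1.960 + 1.282) = 19.85 points, so SE = 19.85·√(2/375) = 1.45. This is solved from the stated power and does not check it independently. It would be 18.3 if two-sided 0.025 had been used. It describes a participant's average over follow-up (AUC/6), not a single visit, which is why the visit SD is varied below.

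**Step 3: put the two effects on one scale.** With p0 = rate/6, the shift that gives 15% fewer episodes is SD × [z(p0) − z(0.85·p0)]. At rate 3.5 that is 19.85 × [z(0.583) − z(0.496)] = 19.85 × 0.221 = 4.39. In reverse, the episode reduction at 18.7 points is 1 − Φ[z(p0) − 18.7/SD]/p0.

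| Control rate | Points equal to 15% fewer episodes, visit SD 19.85 / 25 / 30 | Episode cut at 18.7 points, visit SD 19.85 / 25 / 30 |
|---|---|---|
| 3.5 | 4.39 / 5.52 / 6.63 | 60 / 49 / 42% |
| 3 | 3.75 / 4.73 / 5.67 | 65 / 55 / 47% |
| 2.5 | 3.25 / 4.09 / 4.91 | 70 / 60 / 52% |
| 2 | 2.82 / 3.56 / 4.27 | 75 / 64 / 56% |
| 1.5 | 2.45 / 3.08 / 3.70 | 79 / 69 / 61% |

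**Step 4: power against the margin under the 15% scenario.** Power = Φ[(shift − 14)/SE − 1.96]. At rate 3.5 and SD 19.85 this is Φ[(4.39 − 14)/1.45 − 1.96] = Φ(−8.6), about 4 × 10⁻¹⁸. The most favourable case (rate 3.5, SD 30 throughout, SE = 2.19) gives 5 × 10⁻⁸. With SE 1.45, the margin test needs a true difference of 14 + 1.45 × 1.96 = 16.8 points for 50% power and 18.1 for 80%.

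**Step 5: power against 0 under the same scenario, one-sided 0.025.** If the visit SD and the AUC/6 SD are equal, power is 86, 74, 61, 50 and 39% for rates 3.5 to 1.5, whatever that SD is. If the AUC/6 SD stays at 19.85, power is 57–97% with visit SD 25 and 72–99.5% with visit SD 30.

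**Step 6: how far the assumptions would have to bend.** For 15% fewer episodes to equal 14 points, the visit SD would have to be 63 (rate 3.5) to 114 (rate 1.5). Logistic or t3 shapes at SD 19.85 give smaller shifts, 1.8 to 3.9 points. At rate 3.5, 15% fewer episodes means 0.15 × 3.5/6 = 8.75% of visits change status. If only those visits improved, each would have to fall 14/0.0875 = 160 points to average 14.

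**Step 7: the hypotheses as written.** With H0 ≥ 84 and H1 < 84, rejection shows that the app falls short of the margin. At SE 1.45 and the shifts above, that test would reject more than 99.9% of the time. The lack of power in step 4 therefore refers to the superiority aim in the Power Analysis, not to the test as literally stated under Aim 1.

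**The case against.** A reader might infer that the two power statements assume contradictory effects. The documents do not go that far. They give a detectable difference for each of two separate tests and never say that both describe one effect. The dependence also runs one way: an 18.7-point shift would power both tests. Even in the smallest case above (a 42% cut at rate 3.5), step 1 gives Φ{(51.23 × 0.54 − 4.48)/2.33}, which is effectively 100%.

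A reader might also infer that the plan never addresses less distress. Passing a 14-point margin would imply it, and a margin that the protocol calls minimally clinically significant is a legitimate, stricter choice. The estimate and a one-sided 97.5% CI will be reported. If that is the lower bound, it can be read against 0. What is missing is a prespecified statement that this reading is a test.

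The alpha cost is modest. Giving the episode test the full 0.05 would raise its power from 96.7 to 98.3% at rate 3.5 and from 67.9 to 76.8% at rate 1.5.

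Finally, the SAP replaces Aim 1 with time to first characterisation of risk and quotes the old plan as history. That weakens the practical weight of the point, but the SAP also says the original plan and power analysis were still followed, so the text remains in use.

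**Conclusion.** The point holds in this form: the two primary tests use the same scores but are powered for very different effects. Under a normal, uniform-shift assumption with visit SD 20–30, the 15% episode target is about 2.5–6.6 points, at which superiority over 14 points has essentially no power. The stated 90% belongs to an 18.7-point effect that would cut episodes by roughly 42–79%. The exact figures depend on SDs the documents do not give. The size of the gap does not, as step 6 shows.

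It would be tempting to say that the 90% applies only if episodes fall by 60–79%. That range uses the back-solved 19.85 as if it were a visit-level SD, and the documents do not support that.

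The formal gap is that Hypothesis 1.1 has no margin and the AUC test has nothing else, so a benefit between 0 and 14 points can be reported but not declared. The margin test itself, once its direction is corrected, is valid.

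**What to change.** In Analysis Plan, Aim 1 (Protocol section F, and the SAP alongside the quoted text), replace the single AUC test with a fixed sequence at the one-sided 0.025 already assigned:

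1. H0: AUC_AC − AUC_Cogito ≤ 0 versus > 0.
2. Only if that is rejected, H0: AUC_AC − AUC_Cogito ≤ 84 versus > 84.

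Report the lower one-sided 97.5% bound, from which both steps can be read. The first null is contained in the second and testing stops at the first failure, so no alpha is spent. The same edit corrects the reversed margin hypotheses.

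In Power Analysis (both documents):

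- State the OQ-45 or AUC SD behind the 90%.
- Say that the 90% applies to a true difference of at least 18.7 points and not to the 15% episode scenario.
- Give AUC power against 0 and against the margin under that scenario, with the assumptions used. Do not insert a fixed episode-reduction figure.

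The cost is wording only, with no change to data collection or sample size. The downside is a less favourable power statement for the margin test. The documents do not say whether outcome data had been examined by the SAP date. If they had, the test against 0 should be labelled as added afterwards.

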## **C. Study Design and Research Methods**

**Recruitment.** [name] (Naval Captain, Co-Investigator on grant) will work with US Fleet Forces Command to identify units viable for participation. Members of such units may be serving on larger (e.g., Aircraft Carrier, ~5000 Sailors) or smaller (e.g., Destroyers, ~300 Sailors) vessels. Post-unit identification, [name] will work with commanding officers to facilitate recruitment efforts, in terms of identifying vessels/Sailors. Members of this research team may present information to potential participants. This could occur on the participating vessels and/or identified military locations. Potential in-person options to inform potential participants regarding the study may range from recruitment on-board vessels during redeployment (recruitment and enrollment tables on ships) to pier-side post-leave during redeployment procedures/all-hands meetings to approximately 36 months post-redeployment.

To facilitate remote recruitment, information regarding the study may be provided to Sailors via email or text, or flyers posted around ships/bases. Although distribution of such information may occur via military personnel, responses to such information (e.g., interest in enrollment) will only be directed to members of the study team. In terms of remote recruitment, Sailors can express interest in the study by calling the study team or completing a short recruitment survey in REDCap. The survey will collect name, phone number, and best day/time to contact the Sailor regarding next steps.

**Consent.** Once interest has been noted, potential participants will be asked to provide verbal consent either in person, over the phone, or via a secure and approved video connection

platform (e.g., VA Video Connect, Zoom) to: 1) confirm eligibility and complete informed consent and baseline measures on the MyCAP/REDCap (Research Electronic Data Capture) smartphone app and/or web-based service 2) be randomized; 3) download either the Cogito Companion smartphone app (Experimental) or the MyCAP/REDCap smartphone app and/or web-based service (Active Control); and 4) complete baseline measures. Further information regarding MyCAP/REDCap (<https://projectmycap.org/> or <https://redcapinfo.ucdenver.edu/>) is provided below.

[figure not shown]

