**Authorization.** All required elements of informed consent will be provided on MyCAP/REDCap, including information regarding the purpose of the study, what to expect if participating, possible risks and discomforts, who is paying for the study, the voluntary nature of participating, whom to contact with questions, information regarding the privacy of participants' information, and exceptions to confidentiality. We will request a Waiver of Documentation of Consent and a HIPAA Waiver to facilitate conducting this study.

**Study Design.** Randomized Controlled Trial (RCT), with up to 1,418 individuals being allocated to Experimental (Cogito Companion) or Active Control (MyCAP) based on stratified randomization tables. Randomization will be stratified by gender, force (Surface, Aviation), and smartphone model (Android, I-Phone [once the iOS version is released]), as Cogito algorithms differ based on smartphone platforms. Data is also being collected (feasibility/acceptability) to inform future implementation.

**Study Procedures.** Upon confirming interest in participating in the study, a member of the research team will obtain verbal informed consent and confirm eligibility. Electronic consent will be provided via MyCAP/REDCap. Baseline measures will be administered via MyCAP/REDCap. Military personnel will then be randomized to the Cogito Companion group (Experimental) or the Active Control (MyCAP) group.

Biweekly (every other week) post-consent, study measures will be pushed to participants via the mobile apps (Cogito Companion, MyCAP). Post-completion of measures at the end of the study period (Follow-up Survey), participants will be provided with a link (MyCAP/REDCap). See Figure 1 for an outline of study procedures, and Table 1 for proposed measures and administration schedule.

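### Covariates enter the original OQ-45 models only through a baseline significance test, so precision available from baseline OQ-45 is usually lost in both the episode and the AUC model

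*Protocol*

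**What the plan says.** The Analysis Plan (Protocol section F; same text in the SAP's original plan) tests demographic and clinical characteristics between arms. The default is two-sided 0.05. The rule for covariates then begins "If any variable is found to be significantly different between the groups and is also plausibly associated with an outcome"; a variable meeting both conditions is considered as a potential confounder.

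- Episode model: the count is modelled "as a function of group (0=Active Control, 1=Cogito), any potential confounders, and an offset of log (time"), with negative binomial replacing Poisson if the deviance exceeds 1.5. Episodes are counted "every 2 weeks for weeks 2-12 of the study, inclusive".
- Mixed model for the AUC: longitudinal OQ-45 scores on "group, potential confounders, and an interaction between group and time". The text does not say whether the baseline score is one of the outcome rows, and it does not set the arms' baseline means equal.
- Hypothesis 1.3 inherits both: "The methods employed to address hypothesis 1.1 will be utilized to estimate the difference in number of episodes of each outcome", and likewise for the AUC differences, which include the SF-36.

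Table 1 schedules OQ-45 at baseline. Randomisation is stratified by gender, force and phone type. Neither model's list of terms names baseline OQ-45 or a stratification factor. The SAP introduction says the original analysis plan was still followed after the aims were revised; the revised aims place OQ-45 under the Exploratory Aim.

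**The concern.** In a randomised trial a significant baseline difference is a chance event. It says nothing about how strongly a variable predicts the outcome, which is what determines the precision gained by adjusting for it. The rule therefore discards the likely best predictor of follow-up distress in most realisations of the trial and lets the data choose the covariate set in the rest. The stake is a wider confidence interval for both OQ-45 comparisons, and for the PHQ-9, PCL-5, BSS and SF-36 analyses that reuse the methods.

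**Working it through.** **1. The plan's own figures reproduce.** Inputs from the Power Analysis: N = 750 (375 per arm), rate ratio 0.85, two-sided 0.025 (z = 2.2414). Signorini Poisson-regression power with no overdispersion and no covariates is Φ[(√(N·rate·ln²0.85) − 2.2414·√4) / √(2 + 2/0.85)]. At rate 2.5: √(750 × 2.5 × 0.02641) = 7.037, and (7.037 − 4.483)/2.086 = 1.224, giving 89.0%. Rates 3.5/3/2.5/2/1.5 give 96.7/93.9/89.0/80.7/67.9%, against the stated 97/94/89/81/68%.

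**2. Chance of passing the screen.** P(baseline OQ-45 not flagged) = 1 − 0.05 = 95%. In simulation it was flagged in 4.6-5.5% of trials. Stratification factors are balanced by design, so they would almost never be flagged.

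**3. Episode model.** The documents give no correlations, so visit-to-visit correlation of 0.3/0.5/0.7 is assumed. Set-up: latent normal scores, baseline plus six visits, compound symmetry, threshold set by the control rate, no dropout, 375 per arm, two-sided 0.025, Poisson with robust variance, 5,000 replicates per cell.

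| Control rate | Unadjusted | Plan's screen | Baseline always in |
|---|---|---|---|
| 3.5 | 97/92/82% | 98/93/84% | 99/98/97% |
| 2.5 | 79/67/54% | 80/68/55% | 87/84/78% |
| 1.5 | 49/36/27% | 49/36/27% | 56/50/46% |

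A separate run at rate 2.5 gave 80/68/52% unadjusted and 87/85/78% adjusted. Together: about 80/67/53% against 87/84/78%.

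Extra participants = (mean/SD of the adjusted log rate ratio)² ÷ (same, unadjusted)² − 1. At rate 2.5:
- 375 per arm: 19/41/66% (16/43/57% in the separate run).
- 200 per arm: 19/48/71%. 100 per arm: 18/44/71%. The achieved sample size is not given.
- Baseline less correlated with follow-up than visits are with each other (0.3 against 0.5, 0.5 against 0.7, 0.3 against 0.7): 15/27/11%.

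The ratios 1.188/1.411/1.656 correspond to variance cuts of 1 − 1/ratio = 16/29/40%.

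**4. AUC model.** Generalised least squares, 475 per arm, saturated means, 21% dropout spread over six follow-up visits, same correlations. With a free group term, adding baseline as an outcome row cuts the variance of the week 2-12 contrast by only 1.2/2.0/2.7% (0% with complete data). A common baseline mean cuts it by a further 20/41/64%. These exceed the 16/29/40% for episodes.

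On power: SE = (18.7 − 14)/(1.960 + 1.282) = 1.450, implying an SD of 1.450 × √(375/2) ≈ 19.9, which the plan does not state. If that SD is unadjusted, and taking the superiority direction of the Power Analysis, power = Φ(4.7/(1.450·√(1 − r²)) − 1.960). For r = 0.3/0.5/0.7 between baseline and the averaged follow-up score, this is 92.5/96/99.5%. Visit-to-visit correlation 0.3/0.5/0.7 equals r = 0.46/0.65/0.81, so these AUC powers sit on a more cautious scale than the episode table. If the SD was already a residual SD, some or all of the gain is already in the 90%.

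**5. Type I error (nominal 0.025).** Robust variance, rate 2.5: unadjusted 0.026/0.024/0.025, screened 0.022/0.018/0.016, adjusted 0.024/0.026/0.030. If baseline is added but the plan's deviance switch and model-based errors are kept, rate 1.5 gives 0.026/0.051/0.060. Adjustment usually brings the deviance below 1.5, so ordinary Poisson is retained on counts that are still overdispersed.

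**The case against.** **The test is valid as planned.** This stands. A reader might infer that the rule biases the comparison or that the stated power is wrong; neither follows. Simulated power below the plan's figures reflects overdispersion, a separate matter. Only the differences between columns belong here.

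**The simulated test is not the plan's.** This stands. The plan names no robust variance. Under its own switch with model-based errors, unadjusted power at rate 2.5 was 83/58/36% (400 replicates) instead of 79/67/54%. The powers therefore show the value of adjustment in a test of about the right size; they do not forecast the planned test.

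**The mixed model already uses baseline.** A reader might infer that the loss lies chiefly in the episode model, because baseline may be an outcome row in the other. Step 4 shows otherwise: with a free group term that row adds almost nothing.

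**Other measures may be flagged.** This stands in part. A reader might take the precision to be wholly lost in 95% of trials, but that figure concerns baseline OQ-45 alone. With five baseline measures correlated 0.5-0.7 (assumed), at least one is flagged in about 15-18% of trials. That too is chance, and recovers only part of the loss.

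**OQ-45 is now exploratory.** True under the revised aims, and it limits the consequences. The SAP nevertheless says the original plan was followed, so the rule governs any arm comparison reported from it.

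**Conclusion.** The point holds for the original efficacy analyses. Screening on a baseline significance test is the only stated route into either OQ-45 model, and it usually excludes a baseline score that is already collected. The cost is precision in both models, proportionally at least as large for the AUC. For episodes, fixed adjustment is worth roughly 15-65% more participants at rate 2.5 under the assumed correlations, and about 11% in the least favourable case examined. Every magnitude rests on those correlations, compound symmetry within follow-up and robust variance; the wording of the rule does not. No precision gain is claimed for gender, force or phone type. The revised time-to-risk hypothesis is outside this point because no model is given for it. It should be changed, but it does not threaten validity.

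**What to change.** - Delete the significance-test rule and keep the baseline table descriptive.
- Episode models: pre-specify the baseline value of the outcome concerned (OQ-45, PHQ-9, PCL-5 or BSS) as a fixed covariate. Use robust (sandwich) variance whatever the deviance; without this, adjustment combined with the existing switch can raise type I error to about 0.06.
- Mixed models, including SF-36: enter baseline as a covariate or constrain the arms to a common baseline mean. State whether the AUC window includes baseline. The plan's 14 × 6 = 84 fits six two-week intervals starting at baseline, whereas weeks 2-12 span only five.
- Define baseline as the score taken before randomisation. The Consent text lists baseline measures first alongside eligibility and again after the app download ("and/or web-based service (Active Control); and 4) complete baseline measures"), whereas Study Procedures puts them first ("Military personnel will then be randomized to the Cogito Companion group (Experimental").
- Add gender and force, and phone type only if both platforms were enrolled, so that the analysis matches the randomisation.

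All variables are already collected. Before any comparison by arm, this is a change of wording plus a variance option. If outcomes have already been compared (the SAP is dated 29 May 2023), the cost is one adjusted model per outcome analysis, labelled as a sensitivity analysis.
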